11.3 REPORTING TO HEALTH AUTHORITIES AND IEC/IRB

Adverse event reporting to regulatory agencies and IEC/IRB will be done by the Marketing Authorization Holder (MAH) according to local and international regulatory requirements.

12. PLANS FOR DISSEMINATING AND COMMUNICATING STUDY RESULTS

The rights of the investigator and of the sponsor with regard to publication of the results of this study are described in the investigator contract. As a general rule, no study results should be published prior to finalization of the Study Report.

14. APPENDICES

14.1 ELECTRONIC CASE REPORT FORM

Please refer to “ELECTRONIC CASE REPORT FORM” in site file or in electronic CRF web page for the latest version.

14.2 NON-INTERVENTIONAL STUDY (NIS) ADVERSE EVENT FORM

Please refer to “Non-Interventional Study (NIS) Adverse Event Form” in site file or in electronic CRF web page for the latest version.

14.3 PREGNANCY MONITORING FORM

Please refer to “PREGNANCY MONITORING FORM” in site file or in electronic CRF web page for the latest version.

14.4 ESGLITEO PRESCRIPTION INFORMATION FOR KOREA

Please refer to “ESGLITEO PRESCRIPTION INFORMATION FOR KOREA” in site file or in electronic CRF web page for the latest version.

ANNEX 1. LIST OF STAND-ALONE DOCUMENTS

Number	Document Reference Number	Date	Title
None	None	None	None

Boehringer-Ingelheim
Non-interventional Study Protocol
BI Study Number 1275-0028

c37168579-01

Proprietary confidential information © 2022 Boehringer Ingelheim International GmbH or one or more of its affiliated companies

ANNEX 2. ENCEPP CHECKLIST FOR STUDY PROTOCOLS

Please refer to “ENCePP Checklist for Study Protocols” in separate file

1. INTRODUCTION

The purpose of this statistical analysis plan(SAP) is to describe in detail the plan for statistical analysis method, processing method of data to be used for analysis, and definition of analysis datasets based on the Ministry of Food and Drug Safety's guidelines (2021.11) for final analysis of <1275-0028, 4.0, A regulatory requirement non-interventional study (NIS) to monitor the safety and effectiveness of Esgliteo (empagliflozin/linagliptin, 10/5mg, 25/5mg) in Korean patients with type 2 diabetes mellitus (T2DM), 2022.05.23>,. The table shell and list, which will record the analysis results, will be developed as a separate document. If the analysis is performed in a manner different from this document, the method of change and the reason for change will be recorded in detail in the final report.

2. STUDY OVERVIEW

2.1 STUDY OBJECTIVE

2.1.1 Primary objective

The primary objective of this study is to monitor the safety profile of Esgliteo in Korean patient with T2DM in a routine clinical setting.

2.1.2 Secondary objective

The secondary objective of this study is to monitor the effectiveness of Esgliteo by evaluation of the change from baseline after 12 weeks and/or 24 weeks in the glycosylated hemoglobin (HbA1c), fasting plasma glucose (FPG), body weight, systolic blood pressure (SBP), diastolic blood pressure (DBP) and the final effectiveness evaluation at the end of the last visit in Korean T2DM patients.

2.2 STUDY SIZE

The sample size of 600 patients is based on the requirement of the local regulatory authority, Ministry of Food & Drug Safety (MFDS). As per regulation, long-term surveillance is necessary for the T2DM indication.

CONFIDENTIAL

SD 0400 A v4.0
Statistical Analysis Plan
Protocol No.: 1275-0028

9/38 page

Effective Date: 10-Jan-2022

STATISTICAL ANALYSIS PLAN

Since T2DM is chronic disease it might be restrictive to collect safety and effectiveness data in short-term (12weeks) period, all patients will be enrolled for long-term (24weeks) surveillance.

2.3 MILESTONES

In accordance with local regulation for NIS, interim analyses are planned biannually for the initial two years and annually thereafter.

As per regulation, the re-examination period extends from 31 March 2017 until 30 March 2023. However, active enrolment is to be initiated in 2021 before finalizing the re-imbursement agreement with the authority. Actual study period will be for about 2 years.

Table 1 Milestones

Milestone	Planned Date
Start of data collection	30 Oct 2021
End of data collection	30 Nov 2022
Interim report	30 May 2022
Final report of study results:	30 Jun 2023

3. STUDY POPULATION

A total of 600 patients will be enrolled at approximately 20 sites by as many as 20 or more NIS physicians. To minimize the selection bias, consecutive patients from each site who meet inclusion criteria will be enrolled in this study.

3.1 MAIN DIAGNOSIS FOR STUDY ENTRY

Patients diagnosed with T2DM in Korea. Esglito is indicated as an adjunct to diet and exercise to improve glycemic control in patients with T2DM who are appropriate to take a combination of empagliflozin and linagliptin.

3.2 INCLUSION CRITERIA

- Patients who have started at first time on Esglito in accordance with the approved label in Korea
- Age \geq 19 years at enrolment
- Patients who have signed on the data release consent form

CONFIDENTIAL

STATISTICAL ANALYSIS PLAN

3.3 EXCLUSION CRITERIA

- Patients with previous exposure to Esgliteo
- Patients with hypersensitivity to the empagliflozin and/or linagliptin or any of the excipients
- Patients with type 1 diabetes or diabetic ketoacidosis
- Patients with eGFR < 45 mL/min/1.73m², end stage renal disease, or patient on dialysis
- Patients for whom empagliflozin/linagliptin is contraindicated according to the local label of Esgliteo

3.4 SUBJECTS OF SPECIAL INVESTIGATION

Among the patients who have signed on the data release consent form and the patients who conducted investigation for safety assessment after the administration of Esgliteo, subjects of special investigation (geriatric population (65 years or more), pregnant women, renal impairment, hepatic impairment and other special population, long-term use etc.) will be analyzed.

4. COMPOSITION OF SUBJECTS

A total of 600 patients will be entered in this study, and each patient will be followed for total three times (baseline, short term 12 weeks follow up, Long-term 24 weeks follow up). Since T2DM is chronic disease it might be too restrictive to collect safety and effectiveness data in short-term (12 weeks) period, all patients will be enrolled for long-term (24 weeks) surveillance.

4.1 SUBJECTS WHOSE CRF WAS RETRIEVED

This number means the number of cases who signed the data release consent form to participate in the study as subject, with a record of taking Esgliteo once at least.

4.2 SAFETY SET

These include those who signed the data release consent form to participate in this study as subject, took Esgliteo once at least, and were followed up by the physician once or more. Reflecting MFDS guideline, the cases below shall be excluded from safety analysis set (defined below) in the following order:

CONFIDENTIAL

SD 0400 A v4.0
Statistical Analysis Plan
Protocol No.: 1275-0028

11/38 page

Effective Date: 10-Jan-2022

STATISTICAL ANALYSIS PLAN

- a. Cases not signed or signed on the data release consent form of Esgliteo post-market surveillance (PMS) prior to the contract date
- b. Cases administrated Esgliteo prior to the contract date
- c. Cases administrated Esgliteo prior to the signed on the data release consent form
- d. Not administrated an Esgliteo
- e. Follow-up failure: Patients whose safety information cannot be obtained due to follow-up loss
- f. Violation of efficacy·effectiveness, Dosage
- g. Dual registration
- h. Violation of Inclusion/Exclusion criteria

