9.3.1.3 Number of cases subject to safety evaluation

These include those who signed the data release consent form to participate in this study as subject, took Esglito once at least, and were followed up by the physician once or more. Reflecting Ministry of Food & Drug Safety (MFDS) guideline, the cases below shall be excluded from safety analysis (defined below) set in the following order:

- a. Patients who did not signed or signed on the data release consent form of Esglito PMS prior to the contract date
- b. Patients administrated Esglito prior to the contract date
- c. Patients administrated Esglito prior to the signed on the data release consent form
- d. Patients who have not taken Esglito
- e. Follow-up failure: Patients whose safety information cannot be obtained due to follow-up Loss
- f. Patients who were prescribed for other indications except indications in the local label

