9.5 STUDY SIZE

The sample size of 600 patients is based on the requirement of the local regulatory authority (MFDS). As per regulation, long-term surveillance is necessary for the T2DM indication. Since T2DM is chronic disease it might be restrictive to collect safety and effectiveness data in short-term (12weeks) period, all patients will be enrolled for long-term (24weeks) surveillance.

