9.7.2 Analysis of Safety

- ① Among the subjects of safety evaluation, the number of subjects with adverse event incurred and the number of adverse events incurred should be calculated, and the frequency of adverse events and the 95% confidence interval should be presented.
- ② The number and percentage of adverse events by type and category should be presented.
- ③ Analysis should be made using Chi-square test or Fisher's Exact test on the adverse event onset status by demographic data of subjects of safety evaluation.
- ④ To estimate any factors that are thought to influence the analyzed frequency of adverse events, logistic regression analysis should be conducted, and for statistically significant parameters, the meaning should be described.

Adverse Events (AEs) excluding the AEs whose 'Causality' is "Unlikely" will be treated as AEs whose causality cannot be excluded (hereafter "Adverse Drug Reaction (ADR)").

AEs will be coded according to the latest version of Medical Dictionary for Drug Regulatory Affairs (MedDRA) coding system. Concomitant medications will be coded according to the latest version of KIMS(Korea Index of Medical Specialties) coding system. The study database will not be locked until coding is complete.

Safety analyses will be based on all patients treated, i.e. all patients who received at least one dose of Esgliteo. However, if data for patients who have been treated with Esgliteo beyond the scope of approved label are collected, separate safety analyses will be performed. Patients lost to follow up will be characterized compared to the remaining patients and reason and time point of loss to follow up will be evaluated.

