8.4 SUMMARY OF ADVERSE EVENTS FOR SUBJECTS OF SPECIAL INVESTIGATION

The following types of AEs for each subject of special investigation will be summarized with the number of subjects and proportion of the number of subjects with AE and exact 95% confidence intervals. The details of AEs for each subject of special investigation will also be presented in a listing.

CONFIDENTIAL

STATISTICAL ANALYSIS PLAN

- AE
- ADR
- SAE
- SADR
- UAE
- UADR
- Non-serious adverse drug reaction
- AESI
- Adverse events leading to discontinuation

8.5 SUMMARY OF ADVERSE EVENTS FOR SUBJECTS NOT TREATED ACCORDING TO THE APPROVED LABEL

The following types of AEs for each subject who is treated with Esgliteo beyond the scope of approved label will be summarized with the number of subjects and proportion of the number of subjects with AE and exact 95% confidence intervals. The details of AEs for the subjects will also be presented in a listing.

- AE
- ADR
- SAE
- SADR
- UAE
- UADR
- Non-serious adverse drug reaction
- AESI
- Adverse events leading to discontinuation

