10.5 DETAILS OF SERIOUS UNEXPECTED AEs

The details of Serious Unexpected AEs collected from use result surveillance, special study (Pharmacoepidemiology study, etc.), clinical trials and Spontaneous reporting will be presented in a listing.

11. Changes to the planned analysis method

In the 9.7.1 demographic analysis item of Protocol (version 4.0), it is described that the administration status of this drug (average daily dose) is analyzed, but since Esglito is a composite, the average number of administrations per day will be analyzed.

[figure not shown]
12. SAS program code

The following SAS program codes will be used.

Table 6 SAS program code

Analysis method	SAS program code
Pearson's chi-square test or	PROC FREQ DATA=dataset;
Fisher's exact test	TABLE ae*factor/CHISQ EXACT; RUN;
Paired t-test	PROC UNIVARIATE DATA=dataset; VAR diff;

CONFIDENTIAL

STATISTICAL ANALYSIS PLAN

Analysis method	SAS program code
	RUN;
t-test	PROC TTEST DATA=dataset; CLASS factor; VAR chg; RUN;
ANOVA	PROC MIXED DATA=dataset; CLASS treatment; MODEL variable=treatment; LSMEANS treatment / PDIFF CL; RUN;
Simple logistic regression	PROC LOGISTIC DATA=dataset; CLASS factor; MODEL ae=factor; RUN;
Multiple logistic regression	PROC LOGISTIC DATA=dataset; CLASS factor1 factor2 factor3; MODEL ae= factor1 factor2 factor3 factor4; RUN;

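### SAP 4.2 removes treated, followed-up patients from the Safety set for dosage and eligibility violations (and for dual registration) that the protocol does not list, and SAP Section 11 does not declare the change

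*SAP*

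**What the plan says.** **Protocol 9.3.1.3** admits to safety evaluation patients who consented, took at least one dose and were followed up at least once. It then lists exclusions a to f. The last, (f), is "Patients who were prescribed for other indications except indications in the local label". It has no item for dosage, dual registration or eligibility.

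**Protocol 9.7.2** states the population again, more broadly: "Safety analyses will be based on all patients treated, i.e. all patients who received at least one dose of Esgliteo". It adds that "if data for patients who have been treated with Esgliteo beyond the scope of approved label are collected, separate safety analyses will be performed".

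**SAP 4.2** keeps the protocol's opening definition and items a to e. Item (f) becomes "Violation of efficacy·effectiveness, Dosage". Two items are new: (g) dual registration, and (h) "Violation of Inclusion/Exclusion criteria".

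**SAP 8** runs the safety analyses on the Safety set. **SAP 4.4** draws the long-term safety set from it, and **SAP 4.3** removes from the effectiveness set everyone who is outside it.

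**SAP 8.5** (tables C22 and C23) summarises adverse events in subjects "treated with Esgliteo beyond the scope of approved label".

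**SAP Section 11**, which records changes to the planned analysis, has one entry. It begins "In the 9.7.1 demographic analysis item of Protocol (version 4.0" and concerns average daily dose.

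**The concern.** Safety is the primary objective in both documents, and the protocol's rationale is to observe routine use without the strict entry criteria of randomised studies. A patient who consented, took the drug and was followed up has contributed safety data. If that patient is later found to have breached an entry criterion or the dosing instructions, SAP 4.2 takes the patient and any recorded events out of the main adverse event tables. Protocol 9.3.1.3 does not authorise this, and protocol 9.7.2 points the other way.

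At stake is whether the reported incidences of AEs, ADRs, SAEs and AESIs describe the population that the protocol promised. A reader of the final report would also not learn from SAP Section 11 that the population had changed.

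**Working it through.** There is no planned figure to reproduce: "The sample size of 600 patients is based on the requirement of the local regulatory authority (MFDS"), with no power or precision target. The check is a comparison of texts, followed by an illustration on assumed inputs.

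**1. The two exclusion lists**

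| Item | Protocol 9.3.1.3 | SAP 4.2 |
|---|---|---|
| a–e | consent/contract timing, dosing before contract or consent, not dosed, no safety information | same |
| f | indication outside the label | indication and dosage |
| g | none | dual registration |
| h | none | any eligibility violation |

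Three grounds are new: dosage, dual registration and eligibility.

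**2. Does a version gap explain it?** The SAP cites protocol version 4.0 and the current protocol is 5.0. The 28 Oct 2022 entries in the protocol's amendment log concern dosage text (9.1.2) and adverse event definitions and reporting (11.1, 11.2). None touches the safety set, so the gap does not explain the difference.

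**3. Where do the removed patients' events go?**
- Main tables C1 to C19 and long-term tables C24 to C31: lost, because these rest on the Safety set or a subset of it. (C20 and C21, for subjects of special investigation, fall under the same general rule in SAP 8.)
- C22 and C23: present if the patient was treated beyond the label and if 8.5 is run outside the Safety set. The SAP names no population for 8.5.
- Eligibility violators who are not off-label: no incidence table.
- SAP 10.1 (Appendix 2): counts and reasons for exclusion, but not events.
- SAP 10.4 and 10.5: listings that may catch fatal and serious unexpected events, without incidence.

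**4. Precision is not the issue.** The exact two-sided 95% upper limit for zero events is 0.61% at n = 600, 0.65% at n = 570 and 0.68% at n = 540. Losing 5% or 10% of patients barely moves it. What matters is which events are removed.

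**5. Illustration.** Assumed, because the documents give none of these: k patients removed, SAE risk 2% in the rest, relative risk RR in those removed.

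SAEs lost = k × 0.02 × RR. SAEs kept = (600 − k) × 0.02. All-treated incidence = (lost + kept) / 600. The Safety set reports 2.0% throughout.

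| k | RR | Lost | Kept | Share lost | All-treated incidence |
|---|---|---|---|---|---|
| 6 | 1 | 0.12 | 11.88 | 1.0% | 2.00% |
| 6 | 3 | 0.36 | 11.88 | 2.9% | 2.04% |
| 30 | 0.5 | 0.30 | 11.40 | 2.6% | 1.95% |
| 30 | 1 | 0.60 | 11.40 | 5.0% | 2.00% |
| 30 | 2 | 1.20 | 11.40 | 9.5% | 2.10% |
| 60 | 3 | 3.60 | 10.80 | 25.0% | 2.40% |

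The Safety set understates incidence only when RR exceeds 1. At RR = 1 it is unbiased, and below 1 it overstates. In every row some observed events leave the tables.

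**6. A rare-event case, also assumed.** Six patients with an event among 600 give 1.00% (exact 95% CI 0.37% to 2.16%). If 2 of the 6 are among 30 removed, 4/570 gives 0.70% (0.19% to 1.79%).

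**The case against.** **Protocol 9.7.2 foresees separate off-label analyses.** Off-label dosing could be moved to SAP 8.5 in that spirit, and many eligibility violations are probably label violations too: the first inclusion criterion is label-concordant use, the last exclusion is label contraindication, and the amendment log ties the renal criterion to the label. This stands in part. It narrows the group with no table at all, perhaps to very few. But 9.7.2 does not clearly say that these patients leave the main analysis, and 9.3.1.3 removes only off-indication use.

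**SAP 8.5 is not empty.** A reader might infer that it is, because SAP 8 confines safety analyses to a set from which off-label patients have gone. The documents do not force that reading: a specific section with its own two tables would normally override a general sentence. The fault is an undefined population, not a missing analysis.

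**Prior Esgliteo exposure is a poor example.** One might cite a previously exposed patient as lost through (h). Read literally, protocol item (c) already removes anyone dosed before signing consent, so deleting (h) would not bring that patient back. A treated patient under 19 would be a cleaner case if the label permits such use, but the label is not in the documents.

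**Dual registration need not lose anyone.** Dropping a duplicate record prevents double counting. This stands. The only defect is that the SAP does not say whether one or both records go, or whether their events are merged.

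**Serious events are still visible.** SAEs and AESIs go to the sponsor within 24 hours, and the SAP 10.4 and 10.5 listings state no Safety-set restriction. That limits the harm for signal detection, but it supplies no incidence.

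**The regulator may require the narrower set.** Both lists say they reflect the MFDS guideline, yet they differ, and the guideline is not available here. The fix allows for either answer.

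**Conclusion.** The mismatch is established from the text. The SAP adds dosage, dual-registration and eligibility exclusions that are absent from protocol 9.3.1.3 and contrary to the all-treated wording of 9.7.2, and it does not declare them. Followed as written, it takes observed adverse events in treated, followed-up patients out of the primary-objective tables, and SAP 8.5 repairs this only in part. The protocol contributes to the problem, because 9.3.1.3 already excludes some treated patients whom 9.7.2 would include.

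The size is unknown. The illustrated shift, from 2.0% to at most 2.4%, lies within the exact 95% interval for 12/600 (1.04% to 3.47%) and rests wholly on assumed deviation rates and risks.

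Two stronger readings are tempting. The first is that incidence is biased downwards because the removed patients are at higher risk. Nothing in the documents shows this, and the direction would reverse if their risk were lower. The second is that the exclusions were added after the data were seen, since the signing certificate for the SAP (file name version 2.0) is dated 19 April 2023 and data collection was planned to end on 30 Nov 2022. The documents do not show when items (g) and (h) first appeared, so that inference is not supported either.

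**What to change.** 1. **Safety set.** Align SAP 4.2 with the protocol 9.3.1.3 list by deleting (h) and the dosage part of (f). If the regulator's format needs the narrower set, keep it, declare and justify it in SAP Section 11, and also present the AE, ADR, SAE and AESI summaries on all consented patients with at least one dose and any post-dose safety information. That second population is deliberately wider than the 9.3.1.3 set, so it should be named separately.
2. **SAP 8.5.** State that it is run on all treated patients with off-label use, not on the Safety set.
3. **Dual registration.** Replace exclusion (g) with a rule that keeps one merged record per patient, carrying all adverse events from both records.
4. **Protocol.** Reconcile 9.3.1.3 with 9.7.2, so that one statement defines the safety population and says whether off-label patients are analysed separately in addition to the main tables or in place of them.

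The cost is wording in both documents and, if the narrower set is kept, one extra set of summary tables. No new data are needed.

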4.3 EFFECTIVENESS SET

These cases include those who signed the data release consent form to participate in this study as subject, visited as per the study schedule, took Esgliteo once at least, and were evaluated for the effectiveness.

Reflecting MFDS's guideline, the cases below shall be excluded from effectiveness analysis (defined below) set in the following order.

- a. Cases excluded from safety set
- b. Cases with missing information of effectiveness assessment
- c. Cases omitted in final effectiveness evaluation
- d. Cases whose final effectiveness evaluation was found to be 'Unassessable'

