9.3.1.4 Number of cases subject to effectiveness evaluation

These cases include those who signed the data release consent form to participate in this study as subject, visited as per the study schedule, took Esglito, and were evaluated for the effectiveness.

Reflecting Ministry of Food & Drug Safety (MFDS) guideline, the cases below shall be excluded from effectiveness analysis (defined below) set in the following order:

- a. Patients excluded from safety analysis set listed in section 9.3.1.3
- b. Patients with missing information of assessment of effectiveness set listed in section 9.3.2.2 at visit 2, visit 3

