9. EFFICACY ANALYSIS

Efficacy analyses will be performed on Effectiveness set.

CONFIDENTIAL

STATISTICAL ANALYSIS PLAN

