9.3 THE FINAL EFFECTIVENESS EVALUATION

For the final effectiveness evaluation, the three items ([Improved, Unchanged, Aggravated]) evaluated at the end of the last visit will be summarized using number of subjects, percentage, 95% confidence intervals. In addition, if final effectiveness is evaluated as [Improved], it is classified as [Efficacy]. And If final effectiveness is evaluated as [Unchanged, Aggravated], it is classified as [Inefficacy].

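### SAP 4.3(d) drops patients rated Unassessable from every effectiveness analysis, an undeclared departure from the protocol that can remove measured HbA1c, FPG, weight and blood pressure values

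*SAP*

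**What the plan says.** SAP 4.3 introduces its list with "the cases below shall be excluded from effectiveness analysis (defined below) set in the following order". The first three steps remove (a) patients outside the safety set, (b) those whose effectiveness data are missing, and (c) those with no final evaluation recorded. The last step, (d), removes "Cases whose final effectiveness evaluation was found to be 'Unassessable". SAP 4.5 repeats (b) to (d) for the long-term effectiveness set. SAP section 9 then states: "Efficacy analyses will be performed on Effectiveness set". That covers HbA1c (9.1), the two HbA1c responses, FPG, weight and blood pressure (9.2), and the physician's final evaluation. For the last of these, SAP 9.3 summarises "the three items ([Improved, Unchanged, Aggravated]) evaluated at the end of the last visit".

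Protocol 9.3.1.4 defines the set as consenting patients who "visited as per the study schedule, took Esglito, and were evaluated for the effectiveness". It lists two exclusions: patients outside the safety set, and "Patients with missing information of assessment of effectiveness set listed in section 9.3.2.2 at visit 2, visit 3". Protocol 9.3.2.2.3 defines four grades. Unassessable is the fourth, used when too little information was collected to judge, and the protocol adds that the grade is possible even when objective indicators are present. Protocol 9.7.3, item 4, asks for the number and percentage in all four grades. SAP section 11 lists one change to the planned analysis, the replacement of average daily dose by average number of administrations per day.

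On the minor point, SAP 6.4 settles ties between two Visit 2 results with an example of one result 3 days before and one 3 days after the planned day. Table 4 gives Visit 2 a period of 84, a window of +83 and an accepted range from day 84 to before day 168.

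**The concern.** A global physician rating decides whether a patient's laboratory and physical measurements enter the analysis. HbA1c change is the protocol's primary effectiveness endpoint, and it does not depend on whether the physician could reach an overall judgement. A patient with a baseline and a week-24 HbA1c but an Unassessable rating would stay in the protocol's analysis and drop out of the SAP's. If such patients respond differently from the rest, the reported mean changes and response proportions describe a selected group. The final-evaluation table also loses a category that the protocol requires, so its percentages rest on a smaller denominator. Because section 11 is silent, a reader of the report would have no notice that this departs from the protocol.

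**Working it through.** **1. Set definitions side by side.**

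| Item | Protocol | SAP |
|---|---|---|
| Outside the safety set | excluded (9.3.1.4 a) | excluded (4.3 a) |
| Missing effectiveness information | excluded (9.3.1.4 b) | excluded (4.3 b) |
| Final evaluation omitted | not named separately | excluded (4.3 c) |
| Rated Unassessable | not named | excluded (4.3 d, 4.5 d) |
| Grades tabulated | four (9.7.3) | three (9.3, 9.8) |
| Declared as a change | – | no (section 11) |

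**2. Does the protocol keep these patients?** Its four-grade table is the decisive evidence. If Unassessable patients were outside the protocol's effectiveness set, the fourth row would always be zero. The definition of the grade also allows objective indicators to be present.

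**3. What does (d) remove?** The SAP applies its exclusions in order, so a patient removed at (d) has already passed (b) and (c). That patient has a recorded evaluation and is not counted as having missing effectiveness information. This shows that (d) adds something to (b). It does not show which endpoints were measured, because (b) does not say whether some or all items must be missing.

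**4. Size, by assumption only.** The documents give no share of Unassessable ratings. Let u be that share and g the absolute difference in mean HbA1c change between these patients and the rest.

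- All have an HbA1c value: shift in the mean = u × g.
- Half have a value: shift = g × 0.5u / (1 − 0.5u).

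| u (of 600) | All measured, g = 0.3 to 0.5 | Half measured, g = 0.3 to 0.5 |
|---|---|---|
| 2% (12) | 0.006 to 0.010 | 0.003 to 0.005 |
| 5% (30) | 0.015 to 0.025 | 0.008 to 0.013 |
| 10% (60) | 0.030 to 0.050 | 0.016 to 0.026 |

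These are not bounds. With u = 20% and g = 1.0 the shift is 0.20 × 1.0 = 0.20 points. The sign of the difference is unknown.

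**5. Final-evaluation table.** Suppose 80% of rated patients are Improved (assumed). The three-row table shows 80%. The four-row table shows 80% × (1 − u), which is 78.4%, 76.0% or 72.0% for u = 2%, 5% or 10%. The effective/ineffective rate among rated patients is 80% in both.

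**6. Minor point, SAP 6.4.** Table 4 reproduces: 84 + 83 = 167, so Visit 2 runs from day 84 to day 167 with no minus side. With planned day 84, three days early is day 81. If 12 weeks is instead read as Visit 2 − Baseline = 84, the planned day is 85 and three days early is day 82. Both fall below 84. With planned day 84 no two different days in the range are equidistant from it; with planned day 85 the only tie is day 84 against day 86. The ±3-day example cannot occur under either reading.

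**The case against.** The best defence is that 4.3(c) and (d) only spell out what the protocol already implies. Protocol 9.3.1.4(b) points to section 9.3.2.2, which contains the final evaluation, and Unassessable means that too little information was collected. The protocol also requires that patients were evaluated. This could carry an omitted evaluation, but it does not carry a recorded grade. The protocol lists Unassessable among the outcomes of the evaluation and gives it its own row.

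Both documents say that their exclusion lists reflect the regulator's guideline, which is not available here and may prescribe (d). That remains open. However, the protocol cites the guideline without this exclusion, and a regulatory reason would still need to be declared. The SAP is written against protocol version 4.0, but the amendment log lists no later change to the sections at issue.

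It is also fair to say that protocol 9.7.5, on using all available data, is weak support, since the protocol itself restricts the set. Effectiveness is a secondary objective in a descriptive study, and SAP 10.1 reports exclusions with reasons, so the exclusion will be visible even though its departure from the protocol will not.

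Three stronger readings are tempting and are not supported:

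- **Every Unassessable patient loses measured data.** The protocol says only that objective indicators may be present.
- **The exclusion flatters the drug or inflates the effectiveness rate.** The direction is unknown. The protocol classes Unassessable as neither effective nor ineffective, so leaving it out of that rate is consistent with the protocol.
- **The impossible tie example shows that Visit 2 needs an early tolerance.** The protocol schedules the visit after 12 weeks, which fits Table 4's on-or-after range. Only the example is shown to be inconsistent.

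**Conclusion.** The mismatch is established from the text: the SAP adds an exclusion that the protocol does not name, drops a category that the protocol requires, and does not list either as a change. Measured values are lost only for those Unassessable patients who have them. How many there are, and how far and in which direction the results move, cannot be derived from the documents; every figure in steps 4 and 5 of the working rests on assumed shares, differences and an assumed 80% Improved rate. Under the more modest assumptions the shift in mean HbA1c change is a few hundredths of a point or less. The point is worth correcting because the departure is undeclared and cheap to remove, not because a large bias has been shown. The SAP 6.4 inconsistency is real but of little consequence.

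**What to change.** - Do not use the Unassessable rating to exclude patients from the HbA1c, FPG, weight and blood pressure analyses, in either the main or the long-term set. For each endpoint, include patients who otherwise meet protocol 9.3.1.4 and have a baseline and a post-baseline value.
- In SAP 9.3 and 9.8, report Unassessable as a fourth row, and keep the effective/ineffective rate among rated patients.
- If the regulator's format needs the restricted set, show it as an additional table. Declare any departure that remains in SAP section 11.
- Reconcile the tie example in SAP 6.4 with Table 4.

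The cost is SAP wording, derivation code, one extra row and possibly one extra table, with no new data. The drawback is that the measured endpoints and the effective/ineffective rate will have different denominators, which must be labelled. If the signed SAP is not reissued, SAP section 1 already provides for recording a changed analysis and its reason in the final report.
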